5.0 SELECTION AND ENROLLMENT OF SUBJECTS

5.1 Inclusion Criteria

Establish with patient prior to Informed Consent:

- Adults 18 years of age or older
- HIV-1 infection, as documented by a licensed ELISA test kit and confirmed by a Western blot assay at any time point prior to study entry or at study entry (May do after informed consent if no test results are available).

Off all ARV for \geq three months prior to study entry, no documented evidence of viral resistance, and no evidence of acute HIV infection. For the purposes of this study acute HIV infection will be defined as presence of a detectable HIV-1 viral RNA in the presence of a non reactive HIV-1 or HIV-2 antibody assay or an indeterminate western blot. For the purposes of this study viral resistance is being defined as having a genotypic or phenotypic evidence of resistance or in the absence of formal resistance testing clinical evidence of resistance for e.g. patients with persistent viremia in the face of adequate adherence

- Willingness to use a method of contraception during the study period. Adequate methods of birth control include: condoms, male or female, with or without a spermicide; diaphragm or cervical cap with spermicide; intrauterine device; any of the methods that require a prescription (such as contraceptive pills or patch, Norplant, Depo-Provera, and others) or a male partner who has previously undergone a vasectomy,
- Willingness to have blood drawn
- Non known allergy or contraindication to atorvastatin use
- Ability to understand and willingness to sign the informed consent
- Willingness to have blood stored for future phenotyping and genotyping

After Informed Consent:

- CD4 cell count greater than 350 cells/ml
- 3 viral loads that average greater than 1000 copies/ml within a 4 week period.
- The viral loads will be done using the bDNA method in the NIH laboratory and must be within 20% (log10bDNA of each other).
- A fasting total cholesterol lower than 240mg/dl and a LDL cholesterol lower than 130mg/dl
- Liver function tests (AST or ALT) not greater than 1.5 times the upper limit of normal. Evidence of active hepatitis B or C will not be considered an exclusion criteria if the liver function tests are within normal limits.

- Creatine phosphokinase elevations (CPK) not greater than 3 times the upper limit of normal (ULN) on two sequential determinations and, in the opinion of the investigator, without clear association with exercise.
- Laboratory values:

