5.3.1 Prerandomization evaluations

After signing either the screening/study informed consent, patients will undergo screening tests. Screening will include a complete medical history and physical examination. Laboratory testing will include a fasting lipid profile, flow studies (FACS), routine safety labs which will include a liver function test and creatinine kinase assay, a hepatitis profile and viral load assay to establish baseline viral load. Due to the variability in the viral load assay, we will utilize a minimum of 3 viral load assays to establish a baseline. All testing will need to be completed within a 4 week period prior to randomization. During this period, patients may come in for testing at their own convenience, but testing will not be done more than once within a 24 hour period. All laboratory tests except standard safety labs will be done centrally at SAIC Frederick to maintain consistency. Volunteers at the NIH who satisfy the inclusion criteria and who continue to be interested in the protocol will be now required to sign the study consent.

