5.3.3 Study entry

On the day patients get randomized, patients will undergo routine safety labs including liver function tests (LFT), creatinine phosphokinase, hematological parameters, fasting lipids including apolipoprotein B, hsCRP, plasma HIV viral load and a full FACS. Patients will also have a sample of blood stored for future phenotyping and genotyping. Patients will be required to answer both the Piper Fatigue Scale and the Beck Depression Inventory.

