7.0 STATISTICAL CONSIDERATION

This is a double blind randomized crossover placebo controlled trial of statin use in HIV positive patients with the specific aim of studying the effect of statins on HIV viral load. 22 chronically infected HIV positive patients will be randomized to either atorvastatin 80 mg followed by placebo or placebo followed by atorvastatin (11 per sequence). After 8 weeks of treatment and another 4 weeks washout period, patients in the placebo arm will receive atorvastatin 80mg, whereas patients in the atorvastatin arm will be followed on placebo for another 8 weeks. Table 2 displays the treatment sequence for the two groups.

(Week 0-7)	Week 8-11	(Week 12-19)
Atorvastatin 80mg	Washout	Placebo
Placebo	Washout	Atorvastatin 80mg

Table 2

The effect of lipid lowering agents on HIV-1 RNA levels will be evaluated at the end of 7 weeks and at the end of 19 weeks. The primary goal of this study is to assess the treatment effect by assuming that the carry-over effect is negligible. The primary strength of this cross-over trial is increased efficiency because each patient serves as his or her own control, and the within-subject variability is usually less than the between-subject variability. As a result, the sample size for a cross-over trial will be lower than that for a comparable parallel group design. There is a possible drawback of this design, however, if the carry-over effect cannot be ignored.

Based on historical data we estimate the standard deviation of the log₁₀ viral load as .74 and the correlation coefficient of log₁₀ viral loads before and after treatment as 0.83. To be conservative, a correlation coefficient of 0.75 is used in our calculation. The paired t-test is used

for power calculation. A trial of 20 subjects has a power of 77% (with type I error 0.05) for detecting a 1/3 log₁₀ drop in viral load with atorvastatin. Power to detect a change of 0.4 or 0.5 in log₁₀ viral load based on 10 patients per sequence is 90% and 98% respectively. Thus we have excellent power to detect at least .4 log₁₀ viral load difference by the treatment and reasonable power to detect a 1/3 log₁₀ viral load difference. Due to the possible loss to follow-up (10%), 11 patients will be accrued in each sequence.

At the end of this study, the paired t-test will be used to test this hypothesis. If the underlying distribution is clearly not close to a normal, then the sign-rank Wilcoxon test will be used instead.

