Secondary Objectives for Statistical Consideration

1- To study the difference in the expression of immune activation markers (i.e HLA DR CD38 and Ki67 expression both percentage and number on CD4+ and CD8+ cells) between the end of 7 weeks and the end of 19 weeks in the placebo and atorvastatin sequence. All comparisons of changes between the end of 7 weeks and the end of 19 weeks, i.e. the difference between months 19 and 7 or months 7 and 19 will be conducted by using the paired t-test if the measurements are continuous. McNemar statistic will be used for the changes of discrete markers.

Because of the randomization, the baseline measurements (at beginning of this trial) in placebo and atorvastatin sequences should have the same distribution. This information can be incorporated into an additional statistical analysis, called analysis of covariance ANCOVA. A linear mixed effects model can be used to analyze the difference between the change of viral loads evaluated at the beginning of this trial and at the end of the 7th week, and at the end of 11th week and 19th week in atorvastatin and placebo sequence and placebo and atorvastatin sequence. The difference of viral load at the end of 11th week in two treatment sequences can be used to assess whether there is a treatment carryover effect.

Additional analyses will be conducted to assess whether there is any effect of drug on change viral load, beyond that predicted by the change in LDL.

Finally the correlation between reductions in serum cholesterol and HIV viral load in treatment arm will be assessed by using Spearman's correlation coefficient statistics.

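### The week-11 carry-over check has no baseline adjustment attached: as a raw difference its 95% interval is about ±0.70 log10, and viral loads already collected would narrow it to about ±0.39 to ±0.46

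*Combined protocol and SAP*

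**What the plan says.** Section 7.0 states the assumption openly: "The primary goal of this study is to assess the treatment effect by assuming that the carry-over effect is negligible". It also concedes the risk: "There is a possible drawback of this design, however, if the carry-over effect cannot be ignored". The treatment effect is evaluated at the end of weeks 7 and 19 and tested with a paired t-test.

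Under the secondary objectives of the same section, one paragraph does three things:

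- It notes that randomization should balance the trial-start measurements and says "This information can be incorporated into an additional statistical analysis, called analysis of covariance ANCOVA".
- It offers a linear mixed model for the changes within each period (trial start to week 7, and week 11 to week 19).
- It closes with the carry-over check, a between-sequence comparison: "viral load at the end of 11th week in two treatment sequences can be used to assess whether there is a treatment carryover effect".

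The last sentence names no covariate, estimator, interval or rule for reading the result.

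Pre-treatment viral loads are plentiful. For screening, Section 5.3.1 says "we will utilize a minimum of 3 viral load assays to establish a baseline". Section 5.3.3 adds another sample on the day of randomization, when patients have "plasma HIV viral load and a full FACS" among other tests. The schedule of events (Table 1) has a viral load at day 84, the end of the washout.

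**The concern.** The assumption carries weight. If atorvastatin-first patients still have a residual effect L at week 19, their week-7/week-19 contrast is the true effect minus L. The placebo-first contrast is the true effect, so the average is off by L/2.

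The protocol's background gives a reason to look. Section 2.5 describes a lovastatin study in which 5 of 6 patients showed a changed viral set point 12 weeks after stopping. Twelve weeks is also the gap here between the end of period 1 (day 56) and the end of period 2 (day 140). That study was small, non-randomized and had no untreated comparison, so it motivates a check and proves nothing.

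A raw comparison of 10 patients with 10 carries the whole between-patient spread of viral load. That is the variability the crossover was chosen to avoid. A null result could be taken as support for the assumption when the data could hardly have contradicted it. With adjustment left optional, the choice between a raw and an adjusted check could also be made after the data are seen.

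**Working it through.** **Inputs.** From Section 7.0: SD of log10 viral load 0.74; correlation 0.75 ("To be conservative, a correlation coefficient of 0.75 is used in our calculation"; the historical estimate is 0.83); type I error 0.05; 20 evaluable patients, 10 per sequence. Assumed here: two-sided testing; SD 0.74 also at week 11; and one correlation ρ for every pair of visits. The plan gives only a before/after-treatment correlation.

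**1. Reproduce the plan's own power.** SD of a paired difference = 0.74 × √(2 × (1 − 0.75)) = 0.523. With n = 20 and the noncentral t, two-sided 5%, power is 77.1%, 90.0% and 98.2% for 1/3, 0.4 and 0.5 log10. The plan states 77%, 90% and 98%, so the inputs are read as intended.

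**2. Raw week-11 difference.** SE = 0.74 × √(2/10) = 0.331. With 18 degrees of freedom, half-width = 2.101 × 0.331 = 0.695. Power is 15.9% for 1/3 log10 and 20.9% for 0.4 log10. A difference of 0.98 log10 is needed for 80% power.

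**3. ANCOVA on the mean of k pre-treatment values.** Residual SD = 0.74 × √(1 − kρ²/(1 + (k − 1)ρ)); SE = residual SD × √(2/10); 17 degrees of freedom, t = 2.110. At ρ = 0.75:

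| Adjustment | Residual SD | Half-width | Power, 1/3 log10 | Power, 0.4 log10 |
|---|---|---|---|---|
| none | 0.74 | 0.695 | 16% | 21% |
| one value | 0.489 | 0.462 | 30% | 41% |
| mean of three | 0.422 | 0.398 | 38% | 52% |
| mean of four | 0.411 | 0.387 | 40% | 54% |

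A simulation of 20,000 trials that includes chance baseline imbalance gives slightly lower power: 29%/39%, 37%/49% and 38%/51% for one, three and four values. Type I error stays at 0.05.

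**4. Sensitivity.**

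- With three values, the half-width is 0.50 at ρ = 0.60 and 0.33 at ρ = 0.83.
- If all 22 patients reach week 11, it is 0.66 raw and 0.38 with three values.
- Section 5.1 requires screening viral loads that "must be within 20% (log10bDNA of each other". If that makes them near-duplicates, averaging adds little and the half-width stays nearer 0.46.

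**5. The mixed model of within-period changes.** Suppose L is the same at weeks 11 and 19. The period-2 change in atorvastatin-first patients is then L − L = 0, and the contrast returns the full effect. The price is precision. Each patient's contrast uses four values, so its SD = 0.74 × √(4 × 0.25) = 0.74, SE = 0.74/√20 = 0.165, and half-width is about 2.10 × 0.165 = 0.35. Power for 1/3 log10 is about 48%, against 77% for the paired test. If L decays between weeks 11 and 19, this contrast is biased in the opposite direction.

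**The case against.** The strongest reply is that the raw figures belong to one reading. The carry-over sentence ends a paragraph that has just introduced baseline ANCOVA and a mixed model, so an analyst could fairly adjust the week-11 difference too. With one baseline the half-width is then already 0.46, and the fix gains only the step to about 0.39, or nothing if the screening values are near-duplicates. This stands as far as it goes: the plan is unspecific, not committed to a raw comparison. But both neighbouring methods are offered as options for the treatment effect, and neither is attached to the carry-over check.

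Second, the plan has another safeguard. The L/2 shift applies to the week-7/week-19 contrast, whereas the mixed model compares changes within periods, and Section 3.1 also words the primary objective as a comparison of changes. A constant carry-over cancels there. This stands: it would be wrong to say that the plan leaves carry-over otherwise unaddressed.

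Third, adjustment does not make the check decisive. If only half the target effect (1/6 log10) survived the washout, power would be about 8% raw and 14% with four baseline values. The limit is the sample size. This also stands, and it is why the result should be an interval reported descriptively.

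Fourth, no decision in the trial turns on the check. That is true, and it bears on severity. It does not justify leaving out an adjustment that uses data in hand.

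**Conclusion.** The point holds as a minor improvement. On the literal reading, the check has a half-width of about 0.70 log10, roughly twice the 1/3 log10 target, and power of 16% and 21% for 1/3 and 0.4 log10. One baseline value brings this to about 0.46 (30% and 41%). The mean of three or four brings it to 0.39-0.40 (about 38-40% and 50-54%). These figures rest on SD 0.74 at week 11, 10 evaluable patients per sequence, and ρ = 0.75 between all visits.

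A reader might infer more, and the documents do not support it:

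- **That the primary estimate is biased.** Nothing shows that carry-over occurs, and a residual at week 11 may be gone by week 19.
- **That the paired primary test should be replaced.** The finding gives no reason to change it.
- **That the adjusted check would validate the assumption.** At ρ = 0.75 its half-width still exceeds 1/3 log10, so a difference near zero would not rule out a carry-over of that size. Only near ρ = 0.83 does the half-width with three values reach about 0.33.

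**What to change.** In Section 7.0, replace the closing carry-over sentence with a specified analysis:

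- **Estimate:** the between-sequence difference in log10 viral load at the end of washout (day 84, or the later visit where vaccination has extended the washout), by ANCOVA on each patient's mean pre-treatment log10 viral load (screening values plus randomization day).
- **Reporting:** the adjusted difference with its 95% confidence interval, labelled descriptive. State that its p-value does not decide whether the paired primary analysis is kept.
- **Limits:** state that at a correlation of 0.75 the adjusted check cannot rule out a 1/3 log10 carry-over.
- **Complement:** name the mixed model of within-period changes as a sensitivity analysis. A carry-over that is constant from week 11 to week 19 cancels in it, at lower precision (half-width about 0.35), whereas one that decays over that interval does not.

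The cost is one degree of freedom and the assumption of a linear baseline relation in about 20 patients. No visit, sample, assay or additional test is needed, and the primary analysis and sample size stay as they are.

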8.0 DATA COLLECTION AND MONITORING AND ADVERSE EXPERIENCE REPORTING

8.1 Adverse and Serious Adverse Experience (SAE) reporting

8.1.1 Definition

An adverse event is defined as “undesired and unintended, though not unexpected, result of therapy or intervention”.

An adverse event may also be defined as any “unfavorable and unintended sign (including an abnormal laboratory finding), symptom, or disease temporally associated with the use of an experimental medical treatment or procedure, regardless of whether it is considered related to the medical treatment or procedure. These include both anticipated and unanticipated risk”. A serious adverse event (SAE) is one “that results in death, is life threatening or results in inpatient hospitalization or prolongs the existing hospitalization, results in a persistent or significant disability or incapacity, or results in congenital anomaly / birth defect”. A serious adverse event may not be immediately life threatening or result in death or hospitalization but may jeopardize the patient/study participant or may require intervention to prevent one of the other outcomes listed above.”

8.1.2 Reporting

All adverse events regardless of treatment group or relationship to the drug will need to be reported to the necessary IRB as per their requirements. As reporting requirements are somewhat different at NIAID and NNMC we will follow reporting requirements at both institutions.

All SAE will be reported within 24 hours of when the investigator learns of this event. to both the NIAID and the NNMC IRB. In addition to the above listed event any event that in the investigators judgment is serious even if it does not meet the above criteria will be reported as such.

Adverse events will be graded as per the attached toxicity table in Appendix 1. For toxicities not listed in the table, grading will be based on the schema provided below

- Grade 1: Transient or mild discomfort; no limitation in activity; no medical intervention/therapy required.

- Grade 2: Mild to moderate limitation in activity - some assistance may be needed; no or minimal medical intervention/therapy required.
- Grade 3: Marked limitation in activity, some assistance usually required; medical intervention/therapy required hospitalization possible.
- Grade 4: Extreme limitation in activity, significant assistance required; significant medical intervention/therapy required hospitalization or hospice care.

Adverse events will also be assessed for their relation to study medications and procedures.

Patients coming to the NIH clinical center often travel long distances and are hospitalized for procedures that are routinely done as outpatients at other hospitals. Such elective hospitalizations will not be reported as a SAE or an AE.

For all AEs, the clinician who examines and evaluates the subject will determine the adverse event's causality based upon the temporal relationship to administration of the study agent, the pharmacology of the study agent, and his/her clinical judgment. Terms to describe the degree of causality between the study agent and an event will be definitely, probably, possibly, unlikely related or not related. The best estimate at the time of reporting of the causal relationship between the experimental intervention and an adverse event and the degree of certainty about causality will be graded as follows:

Definitely Related: The adverse event and administration of study agent are related in time, and a direct association can be demonstrated (e.g., disappears or decreases with reduction in dose or cessation of drug/investigational product and recurs with re-exposure).

Probably Related: The adverse event and administration of study agent are reasonably related in time and/or follows a known pattern of response, and the adverse event is more likely explained by study agent than other causes.

Possibly Related: The adverse event and administration of study agent are reasonably related in time and/or follows a known pattern of response, and the adverse event can be explained equally well by causes other than study agent (e.g., could readily have been produced by the subject's clinical state or could have been due to environmental or other interventions).

Unlikely Related: A potential relationship between study agent and the adverse event could exist (i.e., the possibility cannot be excluded), but the adverse event is most likely

explained by causes other than the study agent (e.g., could readily have been produced by the subject's clinical state or could have been due to environmental or other interventions).

Not Related: Adverse event is clearly due to extraneous causes (e.g., underlying disease, environment) or exposure to the investigational product has not occurred. Such events MUST have an alternative, definitive etiology documented in the patient's medical record.

Therefore, a suspected adverse drug/investigational product reaction would be one that is categorized as definitely, probably, possibly, and unlikely related to a study drug/ investigational product".

Please see attached appendix for the toxicity table. All adverse event reporting will end 4 weeks after the end of the study treatment. Any new toxicities not previously reported will be submitted to Med-Watch.

As the study is being done at both the NIAID and at the NNMC reporting requirements for both sites will be followed these include reporting all SAE within 24 hours after becoming aware of a subject death or a potentially life threatening serious adverse event. This will meet the reporting requirements of both the NIAID and the NNMC IRB, as the NIAID requires reporting within 7 days and the NNMC requires reporting within 24 hours of knowledge of death or potentially life threatening SAE. A completed NIAID IRB serious adverse event report will be submitted to the NIAID IRB within 15 days after becoming aware of an inpatient hospitalization (other than elective), a persistent or significant disability/incapacity, or a congenital anomaly/birth defect. Investigators will report within 15 days any other event or condition regardless of grade, which in their judgment represents an event reportable to the IRB. All other serious adverse events will be reported to the NIAID IRB at the time of the annual review. In addition a summary of all adverse events will be reported to the NIAID IRB with submission of a request for continuing review.

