or the last study visit will be extended by 2 weeks. For patients seen at the NIH site, the protocol will not administer routine vaccinations, with the exception of the influenza vaccination. It is anticipated for some patients, participation may overlap with influenza season and that influenza vaccination will be necessary in the event that protocol participation begins prior to but extends into, influenza season. For such patients, standard, inactivated influenza vaccination will be administered (if necessary) during the week 8 visit. For subjects vaccinated during the wash-out phase or at the end of the study the wash-out phase or the last study visit will be extended by 2 weeks. Extension of both these study phases is necessary because of the effects of vaccination on viral kinetics.[33]

Definitions for Schedule of Events – Timing of Evaluations

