5.3.5 Post treatment evaluations

4 weeks after treatment discontinuation (\pm 1 week), patients will have repeat viral load, lymphocyte sub set analysis, immune activation parameters, safety labs including LFTs and creatinine phosphokinase. All visits will be completed on the indicated days of the protocol, for unforeseeable circumstances that might render the patient unable to complete the study visit on the designated days the patient may reschedule within a 2-5 day window except for the end of study visit which may be completed within a 1 week window.

5.4 Subjects can be discontinued from the study for the following reasons:

- Failure to comply with the protocol
- If they develop a serious adverse event (SAE)
- Pregnancy, if a patient becomes pregnant on study; she will stop the study drug and be followed as part of the study through the pregnancy including the peri-partum period to ensure her safety.
- **Any subject with a creatinine phosphokinase (CPK) value greater than 10 times the upper limit of normal (i.e grade 3 or higher), will undergo repeat testing. Repeat testing will be conducted at protocol specified time points (i.e. within 1-3 days of the initial result and also at day 7). Persistently elevated laboratory values, i.e. CPK measurements that remain at the same level or are higher than the initial value, on three consecutive determinations, despite cessation of exercise will result in study drug discontinuation.**
- **In addition, all CPK elevations associated with grade 3 or higher symptoms or for significant symptoms or elevations in CPK that do not fall into either of the above mentioned categories; a conference call with representatives from all three participating sites (either the PI or their designee) will be initiated. Decisions regarding study drug discontinuation for patients meeting the above listed criteria will be made on an individual case by case basis. The medical monitor at the sites will be involved in all decisions regarding study drug discontinuation.**

- Patient develops liver function elevations 3 times the upper limit of normal
- If the serum LDL cholesterol falls to less than 40mg/dl
- Develops a grade 2 or greater allergic reaction to the medicine or develops signs and symptoms of an immediate hypersensitivity reaction to the medication
- Patient needs to start antiretroviral agents using current DHHS guidelines as recommendations.

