- Patient develops any condition that the study investigators deem would be detrimental for the patient to continue on the study
- If the patient desires to leave the study
- Patient starts taking other lipid lowering drugs including fibric acid derivatives, bile acid sequestrants and niacin preparations
- Patients will be dropped from the study if their CD4 count drops by fifty percent on two successive determinations, or falls below 250 cells/ μ l in the absence of any documented ongoing infections/inflammatory processes while on study

If subjects are discontinued from the study secondary to any of the above given reasons they will be replaced according to the prior randomization.

CLINICAL AND LABORATORY EVALUATION

Evaluation*	Screening	Randomization	D7 W1	D14 W2	D42 W6	D56 W8	D84† W12	D91 W13	D98 W14	D126 W18	D140 † W20	D168 W24
Documentation of HIV	Pos ELISA and Confirmatory Blot, previous results will be allowed											
Medical /Medication history	✓	✓	✓	✓	✓	✓	✓	✓	✓	✓	✓	✓
Nadir CD4	✓											
Clinical Assessment	✓	✓	✓	✓	✓	✓	✓	✓	✓	✓	✓	✓
Questionnaires		✓				✓	✓				✓	✓
Physical Exam	✓	✓				✓	✓				✓	✓
Hepatitis profile	✓											
Fasting lipid profile	✓	✓	✓			✓	✓	✓			✓	✓
Markers of inflammation		✓	✓			✓	✓	✓			✓	✓
Hematology	✓	✓		✓	✓	✓	✓		✓	✓	✓	✓
Chemistry including CK	✓	✓		✓	✓	✓	✓		✓	✓	✓	✓
Liver Function Tests	✓	✓		✓	✓	✓	✓		✓	✓	✓	✓
Urinalysis	✓	✓				✓	✓				✓	
Pregnancy Testing	✓	✓	✓	✓	✓	✓	✓	✓	✓	✓	✓	✓
Full FACs	✓	✓	✓			✓	✓	✓			✓	✓
HIV viral load (bdna)	✓ (3 viral load measures will be used to establish baseline)	✓	✓	✓	✓	✓	✓	✓	✓	✓	✓	✓
Statin/placebo		✓	✓	✓	✓	✓	✓	✓	✓	✓	✓	
Stored Plasma/PBMC		✓	✓	✓	✓	✓	✓	✓	✓	✓	✓	✓
Stored Sera		✓				✓	✓				✓	

- * Study consent will be signed at NNMC prior to screening and at randomization at the NIH
- † In the event subject is vaccinated these visits will be extended by 2 weeks

Table 1- Schedule of events

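### Adverse event reporting closes 4 weeks after treatment with no exception, which conflicts with the protocol's own pregnancy follow-up, its SAE rules and its permitted final-visit window

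*Combined protocol and SAP*

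**What the plan says.** The cutoff is in section 8.1.2: "All adverse event reporting will end 4 weeks after the end of the study treatment". It is not limited to non-serious events, and nothing is said about pregnancy or a late final visit. The next sentence sends new, previously unreported toxicities to MedWatch, without timing.

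Other provisions of the protocol bear on the same period:

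- **Pregnancy.** Section 6.1 gives atorvastatin as pregnancy category X. Under section 5.4 a woman who becomes pregnant stops study drug and is to "be followed as part of the study through the pregnancy including the peri-partum period to ensure her safety". Section 6.1 repeats the commitment. Table 1 has a pregnancy test at every visit up to D168.
- **Birth defects.** Section 8.1.1 includes a congenital anomaly in the definition of an SAE. Section 8.1.2 wants every SAE reported within 24 hours of the investigator learning of it. It also wants a completed report to the NIAID IRB within 15 days of awareness for, among others, "a persistent or significant disability/incapacity, or a congenital anomaly/birth defect". Neither clock has an end date.
- **Final visit.** Section 5.3.5 sets it 4 weeks after treatment, plus or minus 1 week, when "patients will have repeat viral load, lymphocyte sub set analysis, immune activation parameters, safety labs including LFTs and creatinine phosphokinase". The same section restricts rescheduling to 2-5 days, "except for the end of study visit which may be completed within a 1 week window". Section 8.1.1 counts an abnormal laboratory result as an adverse event.
- **Vaccination.** Section 5.3 says that after vaccination in the wash-out or at the end of the study, the wash-out "or the last study visit will be extended by 2 weeks". The Table 1 footnote says "In the event subject is vaccinated these visits will be extended by 2 weeks", but its dagger is on D84 and D140, not on D168.

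**The concern.** A single section tells sites to stop all reporting at 4 weeks and also to report SAEs whenever they learn of them. For most events the two rules agree. They part for the outcome of an on-study pregnancy and for anything first seen at a final visit held late but within its window. No order of precedence is given, so a site could take the cutoff as the governing rule. It might then not report a birth defect after exposure to a category X drug, or a liver or CPK abnormality found at a visit the protocol itself allows. The safety profile of atorvastatin is a secondary objective (section 3.2), and section 9.2.2 commits to watching for CNS and optic toxicity for four weeks after drug.

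**Working it through.** **Inputs from the protocol.** Last treatment day D140 and final visit D168 (Table 1); cutoff 4 weeks after treatment (8.1.2); final-visit window ±7 days (5.3.5); vaccination extension 14 days (5.3 and Table 1).

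**1. Planned schedule.** Cutoff = 140 + 28 = D168. This equals the final visit in Table 1 (D168, week 24). Gap: 0 days.

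**2. Final-visit window.** Latest permitted visit = 168 + 7 = D175, and 175 − 168 = 7 days after the cutoff. No outside assumption is needed.

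**3. Vaccination at the end of the study.**
- If only the last visit moves (text of 5.3): 168 + 14 = D182, which is 14 days after the cutoff. With the window as well, 182 + 7 = D189, which is 21 days after.
- If D140 moves (the dagger) and the end of treatment moves with it: end of treatment 140 + 14 = D154, cutoff 154 + 28 = D182, final visit also D182. The extension then adds no gap, and only the 7 days of step 2 remain.

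**4. Pregnancy.** These assumptions are not in the documents:
- Conception on day c, from D−14 (too early for the randomization test) to D168.
- Detection at the first scheduled visit at least 14 days after conception.
- Drug stopped at detection on day s or, if she is not then being dosed, s is the last day of the preceding treatment period.
- Term birth 38 × 7 = 266 days after conception.

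*Cutoff counted from her own drug stop:* gap = (c + 266) − (s + 28) = 238 − (s − c).
- Smallest: the longest interval from conception to stop is 41 days (for example c = D1, found at D42). Birth is at 1 + 266 = D267, the cutoff at 42 + 28 = D70, and the gap is 197 days, about 28 weeks.
- Largest: c = D168, s = D140. Birth is at D434, the cutoff at D168, and the gap is 266 days, 38 weeks. This end belongs to conception after the last dose. For conception on D140 the gap is 406 − 168 = 238 days, 34 weeks.

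*Cutoff fixed at D168:* gap = c + 266 − 168 = c + 98. This runs from 84 days (12 weeks) at c = D−14 to 266 days (38 weeks) at c = D168.

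*Sensitivity to birth date.*

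| Birth after conception | Days past cutoff, own drug stop | Days past cutoff, fixed D168 |
|---|---|---|
| 38 weeks | 197 to 266 | 84 to 266 |
| 35 weeks | 176 to 245 | 63 to 245 |
| 22 weeks | 85 to 154 | −28 to 154 |

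Only the last cell reaches below zero. At 22 weeks the fixed-D168 gap is c + 154 − 168 = c − 14, so a birth inside the window needs conception before D14 as well as extreme prematurity.

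**The case against.** The strongest reply is that the specific rule governs the general one. The 24-hour and 15-day SAE rules run from awareness and do not expire. Section 8.1.2 also lets the investigator report any other event judged reportable, and it has the MedWatch sentence. Sections 8.1.2 and 8.2 bind the sites to both IRBs' requirements, to ICH/GCP and to applicable regulation. A sensible site might well report a birth defect regardless. This stands against any inference that a birth defect could never be reported. It does not remove the conflict, because none of these provisions is written as an exception to a sentence that covers all reporting.

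On the final visit, the cutoff and the visit coincide by design, so a gap needs a late or extended visit. Nor does section 8.1.2 say whether the cutoff applies to onset or to the date of report, so an event that began before D168 but was seen later is not clearly excluded. Both points are fair, and the second is a further ambiguity to settle.

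A reader might infer that findings from vaccinated participants always fall outside the window. The documents do not support that, because the Table 1 dagger may move the end of treatment too. Protocol-administered vaccination at the end of the study is also described only for the DOD sites.

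A reader might also infer that the atorvastatin safety comparison is distorted, because the last 4 weeks follow atorvastatin only in the placebo-first sequence. That is not shown. The sentence concerns reporting, while final-visit laboratory tests remain scheduled and recorded on case report forms (section 8.4). In the atorvastatin-first sequence, participants are still followed in weeks 12 to 24, from day 29 after atorvastatin onward.

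Finally, the trial has 22 participants with required contraception, so a pregnancy is unlikely. That limits the weight of the point, not its correctness.

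**Conclusion.** The point holds as a conflict between stated rules that must be reconciled; it is not a proven bar to reporting. For pregnancy, the cutoff precedes a term birth by about 28 to 38 weeks counted from the woman's own drug stop, or about 12 to 38 weeks counted from a fixed D168. These figures rest on the assumed 38 weeks to term and on the detection rule in the working. Only an extremely preterm birth after conception near randomization could come before a fixed D168. For the final visit, the gap is up to 7 days from the protocol's own window. It becomes 14 to 21 days only if the vaccination extension moves the last visit alone. The consequence is that late safety findings and birth defects may go unreported if a site lets the cutoff prevail. The primary viral load analysis and the sample size are unaffected.

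**What to change.** Replace the cutoff sentence in section 8.1.2 so that:

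- AE and SAE reporting runs to the later of 4 weeks after the last dose and the participant's actual final visit, including its window and any vaccination extension.
- For any on-study pregnancy, pregnancy outcome and congenital anomaly are collected and reported, for mother and infant, through the peripartum follow-up already promised in sections 5.4 and 6.1.

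The new sentence should also say whether the limit refers to onset or to report date. Separately, reconcile section 5.3 with the Table 1 footnote on which visits the vaccination extension moves.

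The cost is protocol wording, plus reporting work for at most a few participants. The final visit and the pregnancy follow-up are already planned, so no visit is added.
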